8.9 Reporting Product Complaints

Any defects with the investigational products must be reported *immediately* to NextCure by the site with further notification to the site monitor. During the investigation of the product complaint, all investigational products must be stored per instructions in pharmacy manual unless otherwise instructed. NextCure contact information for reporting product complaints:

[REDACTED]
[REDACTED]
[REDACTED]
[REDACTED]
[REDACTED]
[REDACTED]

9 STATISTICS

Tabular summaries will be presented by dose groups. Categorical data will be summarized by the number and percentage of subjects in each category. Continuous variables will be summarized by descriptive statistics including mean, standard deviation, median, minimal, and maximal values. All analyses, unless specified otherwise, will be based on as-treated population, which includes all subjects who receive any dose of NC762. Additional details of statistical analyses will be described in the Statistical Analysis Plan (SAP).

9.1 Study Populations

The full analysis set (FAS) includes all subjects enrolled in the study who received at least one full dose of NC762. This population will be used in all the summaries and analyses except for the of safety analysis set (SAS) and PK. The SAS will include all the subjects who receive any amount of study drug. The summaries and analyses of safety data will be performed on the SAS. The PK analysis set (PAS) will include all the subjects whose blood samples are collected for PK analysis. The PK data summaries and analyses will be performed on the PAS.

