5.4.8 Management of Infusion Reactions

Table 6 shows treatment guidelines for subjects who experience an infusion reaction associated with administration of study drug. Signs and symptoms usually develop during or shortly after drug infusion and generally resolve completely within 24 hours of completion of infusion.

Table 6: Infusion Reaction Treatment Guidelines

NCI CTCAE v5.0 Grade/Severity	Treatment	Premedication at Subsequent Dose Administration
Grade 1: Mild reaction; infusion interruption not indicated; intervention not indicated.	Increase monitoring of vital signs as medically indicated until the subject is deemed medically stable in the opinion of the investigator.	None.
Grade 2: Requires infusion interruption but responds promptly to symptomatic treatment (e.g., antihistamines, nonsteroidal anti-inflammatory drugs (NSAIDs), narcotics, IV fluids); prophylactic medications indicated for ≤ 24 hours.	
Stop infusion and monitor symptoms. Additional appropriate medical therapy may include but is not limited to the following:
 
 • IV fluids • Antihistamines • NSAIDs • Acetaminophen • Narcotics 
Increase monitoring of vital signs as medically indicated until the subject is deemed medically stable in the opinion of the investigator. If symptoms resolve within 1 hour of stopping drug infusion, the infusion may be restarted at 50% of the original infusion rate. Otherwise, dose administration will be interrupted until symptoms resolve, and the subject should be premedicated for the next scheduled dose.
 
Subjects who develop Grade 2 toxicity despite adequate premedication should be permanently discontinued from further study drug administration.
	
Subject may be premedicated 1.5 h (± 30 min) prior to infusion with the following:
 
 • Diphenhydramine 50 mg orally (or equivalent dose of antihistamine). • Acetaminophen 500-1000 mg orally (or equivalent dose of antipyretic).

NCI CTCAE v5.0 Grade/Severity	Treatment	Premedication at Subsequent Dose Administration

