
Grade 3: Prolonged (i.e., not rapidly responsive to symptomatic medication and/or brief interruption of infusion); recurrence of symptoms following initial improvement; hospitalization indicated for other clinical sequelae (e.g., renal impairment, pulmonary infiltrates). or Grade 4: Life-threatening; pressor or ventilatory support indicated.
	
Stop infusion. Additional appropriate medical therapy may include but is not limited to:
 
• IV fluids• Antihistamines• NSAIDs• Acetaminophen• Narcotics• Oxygen• Pressors• Corticosteroids• Epinephrine 
Increase monitoring of vital signs as medically indicated until the subject is deemed medically stable in the opinion of the investigator. Hospitalization may be indicated. Subject is permanently discontinued from further study drug administration.
	No subsequent dose.

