9.5.3 Efficacy Analyses

The response will be assessed by CT/MRI image during screening and every 8 weeks (56 \pm 7 days) post-dosing for 6 months and then every 12 weeks (84 \pm 7 days) thereafter. The efficacy study endpoints include ORR, DCR, DoR, PFS, and OS. Tumor response will be determined according to RECIST v1.1. Time-to-event data (DoR, PFS, and OS) will be analyzed using the Kaplan-Meier method. All the efficacy data will be summarized by phase, dose group, and cohort.

- ORR includes RECIST v1.1 complete and partial response (CR or PR). ORR with 95% exact confidence interval (CI) will be summarized by phase, dose group, and cohort.
- DCR includes RECIST v1.1 complete, partial response, and stable disease (CR, PR or stable disease lasting 24 weeks or longer). DCR with 95% exact CI will be summarized by phase, dose group, and cohort.
- DoR is defined as the duration from the first documented ORR to the first documented progressive disease or death due to any cause, whichever occurs first. For subjects who are alive and progression-free at the time of discontinuation from study, data cutoff for analysis, or use of other anticancer drug, DoR will be censored at the last tumor assessment date.

The DoR will only be analyzed for the subgroup of subjects with an objective response.

DoR = (progressive disease, death, or censored date) – (date of first response + 1)

- PFS is defined as from starting study treatment to the first documented progressive disease or death due to any cause, whichever occurs first. For subjects who are alive and progression-free at the time of discontinuation from study, data cutoff for analysis, or use of other anticancer drug, PFS will be censored at the last tumor assessment date.

PFS = (progressive disease, death, or censored date) – (date of first dose of study drug + 1)

- OS is defined as from starting study treatment to death due to any cause. For subjects who are alive will be censored at the date of last known alive (LKA).

OS = (Death or LKA date) – (date of first dose of study drug + 1)

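### The efficacy set requires one full dose of NC762, so a treated subject who never completes an infusion leaves the ORR, DCR, PFS and OS analyses

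*Combined protocol and SAP*

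**What the plan says.** Section 9.1 defines the FAS as "all subjects enrolled in the study who received at least one full dose of NC762" and gives it a wide scope: "This population will be used in all the summaries and analyses except for the of safety analysis set (SAS) and PK". Efficacy therefore falls on it. The criterion is one full dose at any cycle, not a full first infusion. The term full dose is not defined.

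The safety set in the same section is broader: "The SAS will include all the subjects who receive any amount of study drug". The opening paragraph of Section 9 sets a general default that is also broader: "All analyses, unless specified otherwise, will be based on as-treated population, which includes all subjects who receive any dose of NC762".

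Section 9.5.3 lists ORR, DCR, DoR, PFS and OS. It says "ORR with 95% exact confidence interval (CI) will be summarized by phase, dose group, and cohort", but names no analysis set for any of them. It measures PFS and OS from the date of first dosing.

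Table 6 (Section 5.4.8) covers stopped infusions. For a Grade 3-4 reaction the infusion is stopped and "Subject is permanently discontinued from further study drug administration". For a Grade 2 reaction, "If symptoms resolve within 1 hour of stopping drug infusion, the infusion may be restarted at 50% of the original infusion rate"; failing that, the subject waits for the next planned dose with premedication. A Grade 2 reaction that recurs despite premedication ends treatment.

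**The concern.** An efficacy set should not depend on what happens after treatment begins, least of all on how well the drug is tolerated. Under Section 9.1, a subject whose first infusion is stopped for a Grade 3-4 reaction has been treated, counts for safety, and can never qualify for the FAS. The reason for leaving is an effect of NC762. Such a subject is unlikely to be recorded as a responder, so the exclusion would usually push ORR and DCR upward.

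It also sits badly with the time-to-event definitions. If this subject dies, the death is an OS and PFS event on a clock that starts at first dosing, yet the subject is absent from the set in which those endpoints are analysed.

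The study is open-label, with response read by investigators and no central imaging vendor (Sections 1.3.4 and 7.6.1.1.2). With full dose undefined and no set named in Section 9.5.3, the denominator could be settled after responses are known.

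**Working it through.** The plan states no figure for this point, so there is none to reproduce. The check has two parts.

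**Who is excluded.** Reading Section 9.1 against Table 6:

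- Grade 2 reaction at the first infusion, restarted and completed: a full dose is possible, so the subject can enter the FAS.
- Grade 2 reaction, not restarted, next dose completed: the subject enters the FAS.
- Grade 2 reaction, not restarted, then a further Grade 2 reaction despite premedication that stops the next infusion: treatment ends and the subject is excluded.
- Grade 3-4 reaction at the first infusion, stopped before completion: no further dose, so the subject is excluded.
- Grade 3-4 reaction at a later infusion, after at least one complete dose: the subject remains in the FAS.

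Only subjects who never complete any infusion are lost.

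**Size of the effect on ORR.** Inputs: n = 24 treated per tumor type (the Phase 2 maximum in Section 9.2.2); x responders and k excluded non-responders, both assumed because the documents give no rate.

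- ORR in all treated = x/n
- ORR in the FAS = x/(n - k)
- Ratio = n/(n - k) = 1/(1 - f), with f = k/n

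With x = 4 (95% exact CI in brackets):

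| k | FAS | All treated | Difference (points) | Ratio |
|---|---|---|---|---|
| 0 | 4/24 = 16.7% (4.7-37.4) | 16.7% | 0 | 1.00 |
| 1 | 4/23 = 17.4% (5.0-38.8) | 16.7% | 0.7 | 24/23 = 1.04 |
| 2 | 4/22 = 18.2% (5.2-40.3) | 16.7% | 1.5 | 24/22 = 1.09 |
| 3 | 4/21 = 19.0% (5.4-41.9) | 16.7% | 2.4 | 24/21 = 1.14 |

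With x = 6, the FAS value is 25.0%, 26.1%, 27.3% and 28.6% for k = 0 to 3, against 6/24 = 25.0% throughout.

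If an excluded subject is replaced so that 24 remain in the FAS, the same formula applies with a larger treated total. With 4 responders and one excluded, the FAS gives 4/24 = 16.7% against 4/25 = 16.0% of those treated.

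**Small groups.** Section 9.5.3 also reports ORR by dose group, and Section 3.1.1.1 plans 3 to 6 evaluable subjects per Phase 1a dose level. One responder among 6 treated is 1/6 = 16.7%; with one non-responder excluded it is 1/5 = 20.0% (ratio 1.2). Among 3 treated, 1/3 = 33.3% becomes 1/2 = 50.0% (ratio 1.5).

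**Direction.** The rise depends on the excluded subject being a non-responder. If the excluded subject were one of the 4 responders, the FAS would give 3/23 = 13.0% against 4/24 = 16.7%.

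**Other endpoints.** DCR follows the same formula if the excluded subject does not have disease control. For PFS and OS the documents give nothing from which a size could be computed. What can be said is that an event or censoring time belonging to a treated subject is dropped.

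**The case against.** Three stronger readings are tempting, and the documents do not support them.

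- A reader might infer that Sections 9 and 9.1 contradict each other and give two denominators for one table. They do not. The any-dose default yields wherever another rule is specified, and Section 9.1 specifies one. The weakness is that, with safety, PK and everything else assigned in Section 9.1, the default has almost nothing left to govern.
- A reader might infer that every subject whose first infusion is stopped drops out. Table 6 lets a Grade 2 infusion restart, or a later dose follow, and one full dose at any cycle is enough.
- A reader might infer that ORR is biased upward as a matter of fact. That needs at least one never-completed subject who does not respond. With none there is no effect.

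The case for leaving the plan alone also has weight. Efficacy is secondary and Section 9.3 plans no formal test. The exact interval for 4/24 spans about 33 points (37.4 - 4.7), far more than the shift. Stage 1 continuation depends on a count of responses, which does not change when a non-responder leaves a denominator. Whether such a subject would be replaced is a separate matter, because Section 3.1.2 counts evaluable subjects without defining the term for response. The FAS does not itself require a post-baseline scan, and Section 9 defers further detail to a SAP, which could settle some of this.

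These points limit the size and the importance. They do not justify the exclusion: the rule is stated in Section 9.1, it removes treated subjects because of a post-treatment event, and nothing in the text gives a reason for it.

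**Conclusion.** The point stands in a narrow form. Section 9.1 removes from the efficacy analyses any treated subject who never completes an infusion, chiefly one stopped by a Grade 3-4 reaction at the first dose. If such subjects occur and do not respond, ORR is overstated by 1/(1 - f). For a cohort of 24 with 4 responders, that is 0 to 2.4 percentage points for 0 to 3 excluded subjects, well inside the confidence interval. The relative effect is larger in Phase 1a dose groups. The responder and exclusion counts are assumptions, and no size can be given for PFS or OS.

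The primary safety endpoint is unaffected because it uses the any-amount safety set. This is an inexpensive correction worth making before data are reviewed, not a flaw that undermines the study.

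**What to change.** - In Section 9.1, define the FAS as all subjects who received any amount of NC762. It then agrees with the safety set and with the default in Section 9, which can stay or be removed as redundant.
- In Section 9.5.3, name that set for ORR, DCR, PFS and OS. DoR stays restricted to responders within it.
- State that treated subjects without a post-baseline scan count as non-responders for ORR and as not having disease control for DCR. The present FAS does not exclude for a missing scan, but the wider set will contain subjects who stop at the first infusion, and Section 9.5.3 does not say how to classify a subject with no scan.
- Keep the full-dose set as a sensitivity analysis, with full dose defined.

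The cost is a few lines of protocol or SAP text. No extra data, subjects or procedures are needed and no treatment rule changes. ORR may be slightly less favourable.

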9.2 Selection of Sample Size

A maximum of 170 eligible subjects in Phase 1 and Phase 2 (50 + 120) will be included in this study.

9.2.1 Sample Size for Phase 1

The primary objective of the dose escalation part in Phase 1 of the study (Phase 1a) is to determine the MTD or PAD of NC762. A 3 + 3 study design will be used for dose escalation. A maximum of 5 dose levels will be tested. Therefore, a maximum of 30 subjects, who are evaluable for DLTs, will be included in the dose escalation phase. Subjects evaluable for DLTs are defined as the subjects who take a full dose of NC762 and then are followed up for 28 days for assessment of DLTs. Any subjects who do not meet the criteria will be replaced.

Phase 1 of the study may also include safety expansion cohorts (Phase 1b) evaluating doses and schedules equivalent to or lower than the highest dose levels determined to be safe and/or doses determined to be pharmacologically active. Each safety expansion cohort will enroll up to an additional 10 evaluable subjects (total of 20 subjects in the Phase 1b). If < 3 of 10 evaluable subjects experience a DLT, the cohort will be deemed safe. If more than 1 safety expansion cohort is deemed safe, then the RP2D will be determined in conjunction with the investigators and sponsor based on all available safety, PK, PD, and biomarker results.

9.2.2 Sample Size for Phase 2

Phase 2 of the study will further evaluate the safety, tolerability, preliminary efficacy, PK, and pharmacologic activity of the recommended dose of NC762. The sample size for each tumor type will be guided by the Simon 2-stage design (Simon, 1989). Let 5% be a clinically insignificant response rate for all tumor types. During Stage 1, 12 subjects will be enrolled; if no responses are observed, then the cohort will be discontinued. If at least 1 response is observed, then 12 additional subjects will be enrolled (Stage 2), for a maximum of 24 subjects per tumor type in Phase 2. The detailed calculation is based on a 1-sided Type I error of 0.05 and power of 80% to detect a 25% response rate for each of the tumor types.

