Subjects who drop out for reasons other than a DLT (e.g., events clearly associated with the underlying disease, disease progression, concomitant medication, withdraw of consent, or comorbidity) during the 28-day DLT observation period will be considered non-evaluable and will be replaced. Dose modifications should not be made during the DLT observation period without discussion with the medical monitor. Intrasubject dose escalation is not permitted; however, once the recommended Phase 2 dose (RP2D) and schedule has been determined, ongoing subjects in Phase 1 may be permitted to escalate to the RP2D with approval of the medical monitor assuming the subject has not experienced \geq Grade 3 toxicity in previous treatment cycles. The cohorts and dose levels are shown in the table below.

Cohort	Dose of NC762
1 (Starting dose)	0.5 mg/kg
2	1.5 mg/kg
3	5.0 mg/kg
4	10 mg/kg
5	20 mg/kg

Phase 1b – Safety Expansion

To evaluate additional PD activity of NC762 and confirm the preliminary safety of the dose escalation cohorts, Phase 1 of the study will include safety expansion cohorts (denoted as Phase 1b) evaluating doses and schedules equivalent to or lower than the highest dose levels determined to be safe and/or doses determined to be pharmacologically active. All doses and schedules explored during the safety expansion will depend on PK, PD, biomarker, and safety results.

Approximately 20 evaluable subjects will be enrolled in the Phase 1b safety expansion, with each dose cohort enrolling up to 10 additional subjects. If < 3 of 10 evaluable subjects

experience a DLT, the cohort will be deemed safe. If > 1 safety expansion cohort is deemed safe, then a recommended dose and schedule will be determined in conjunction with the investigators and sponsor based on all available safety, PK, PD, and biomarker results. The safety expansion cohorts may be conducted in parallel to Phase 2 and may be limited by the sponsor to subjects with specific tumor types to achieve a balance across cohorts.

[figure not shown]
Phase 2 – Dose Expansion

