3.1.1.1 Phase 1a - Dose Escalation

In Phase 1a, subjects with advanced or metastatic solid tumors who progressed after treatment with available therapies that are known to confer clinical benefit, who are intolerant to treatment, or refuse standard treatment will be enrolled. A 3 + 3 design will be utilized to determine the MTD or PAD of NC762.

A minimum of 3 evaluable subjects will be enrolled in each cohort beginning with Cohort 1 (0.5 mg/kg; starting dose). The first 3 evaluable subjects within a cohort will be observed for a DLT observation period of 28 days before the next cohort begins enrollment. Only one subject can be dosed on the first day of dosing for each cohort (additional subjects can begin dosing in ≥ 48 hours). The dose will be escalated if 0 of the first 3 evaluable subjects enrolled has a DLT. If 1 of

the first 3 evaluable subjects enrolled has a DLT, then the cohort will be expanded to include 3 additional evaluable subjects, and if no DLT occurs in the additional 3 subjects, then the dose will be escalated. If a DLT occurs in one-third or more of the expanded cohort, then the MTD will be deemed to be exceeded and the previous dose level will be considered the MTD. Intermediate dose levels below the MTD may be explored pending safety review.

If only 3 subjects were treated at the MTD or PAD, then a minimum of 3 additional evaluable subjects will be enrolled at this dose before it is administered in Phase 2 of the study.

If starting dose exceeds the MTD, the sponsor and investigators will consider dosing NC762 at a lower dose, and/or investigate 0.5 mg/kg at alternate dose schedules, based on available safety, PK, PD, and biomarker data. If an alternate schedule is determined to be safe, re-escalation of NC762 will proceed according to Table 2.

Throughout the treatment period, if > 33% of subjects (a minimum of 6 subjects) experience a \geq Grade 3 toxicity related to study drug after completing \geq 4 cycles, then dose administration will be stopped, and the MNTD will be determined in conjunction with the investigators and sponsor based on all available safety data.

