Additional subjects will be enrolled in a cohort to achieve the minimum of 3 evaluable subjects. Subjects who drop out for reasons other than a DLT (e.g., events clearly associated with the underlying disease, disease progression, concomitant medication, or comorbidity) during the 28-day DLT observation period will be considered non-evaluable and will be replaced. Dose modifications should not be made during the DLT observation period without discussion with the medical monitor. Intrasubject dose escalation is not permitted; however, once the RP2D and schedule has been determined, ongoing subjects in Phase 1 may be permitted to escalate to the RP2D only with approval of the medical monitor assuming the subject has not experienced \geq Grade 3 toxicity in previous treatment cycles. The cohorts and dose levels are shown in Table 2.

Table 2: NC762 Dose Levels and Cohorts

Cohort	Dose of NC762
1 (Starting dose)	0.5 mg/kg
2	1.0 mg/kg
3	5.0 mg/kg
4	10 mg/kg
5	20 mg/kg

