3.3.2 Replacement of Subjects

Subjects may be replaced for any of the following reasons:

- In Phase 1, any subject who withdraws from treatment before the completion of the DLT period for any reason other than a DLT (e.g., subject is not evaluable for DLTs)
- In Phase 1b and Phase 2, a subject who has not met the biopsy requirements for the study (i.e. pre-treatment samples) will not be eligible to enroll
- Subject does not meet the eligibility requirements of the study (accidental enrollment)

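### Section 9.2.1 defines DLT-evaluable subjects without keeping those who had a DLT, so read literally it replaces some of the most severe DLTs and conflicts with the synopsis and Sections 3.1.1.1 and 3.3.2

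*Combined protocol and SAP*

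**What the plan says.** Section 9.2.1 gives the protocol's only positive definition of DLT evaluability: "Subjects evaluable for DLTs are defined as the subjects who take a full dose of NC762 and then are followed up for 28 days". It continues: "Any subjects who do not meet the criteria will be replaced". There is no alternative for a subject who had a DLT.

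The design sections use a different rule. The synopsis and Section 3.1.1.1 cover "Subjects who drop out for reasons other than a DLT"; such subjects, if they leave during the "28-day DLT observation period will be considered non-evaluable and will be replaced". The synopsis gives as examples of non-DLT reasons "disease progression, concomitant medication, withdraw of consent, or comorbidity"; Section 3.1.1.1 has a similar list without consent withdrawal. Section 3.3.2 allows Phase 1 replacement of "any subject who withdraws from treatment before the completion of the DLT period for any reason other than a DLT".

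The decision rules count evaluable subjects. In Section 3.1.1.1: "The dose will be escalated if 0 of the first 3 evaluable subjects enrolled has a DLT". In Section 9.2.1, for Phase 1b, if fewer than 3 "of 10 evaluable subjects experience a DLT, the cohort will be deemed safe".

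Section 5.4.2 bases escalation on events from the first day of drug administration and sets no full-dose condition.

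**The concern.** A definition that requires both a complete dose and complete follow-up fails exactly those subjects whose toxicity prevents one or the other. Two cases follow from the protocol's own tables.

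- **(a) First infusion stopped by a Grade 3 or 4 reaction.** Table 6 stops the infusion and ends study drug for good, so the subject never takes a full dose. The event is a nonhematologic toxicity of Grade 3 or higher, hence a DLT under Table 3.
- **(b) DLT death before Day 28.** Table 3 counts a death not clearly due to the disease or extraneous causes. Twenty-eight days of follow-up cannot be reached.

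Under 9.2.1 both subjects are replaced; under the synopsis, 3.1.1.1 and 3.3.2 they are not replaceable. The error can run only one way. One such replacement can turn 1 of 3 (expand) into 0 of 3 (escalate), or 3 of 10 (not safe) into 2 of 10 (safe). In a first-in-human study these are among the events that matter most to the decision.

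**Working it through.** **The plan's own figure.** Five dose levels (9.2.1) times at most 6 evaluable subjects per level (3 + 3) gives 5 × 6 = 30, the stated Phase 1a maximum. The issue is who is counted, not how many.

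**The two rules side by side.**

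| Subject | Section 9.2.1 | Synopsis, 3.1.1.1, 3.3.2 |
|---|---|---|
| DLT after a full dose, stops drug, followed to Day 28 | evaluable | not replaced |
| (a) DLT reaction stops first infusion | replaced (no full dose) | not replaced |
| (b) DLT death before Day 28 | replaced (no 28-day follow-up) | not replaced |
| DLT, then consent withdrawn or lost to follow-up before Day 28 | replaced | unclear |

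The first row covers most toxicity withdrawals, because Section 5.5.1 keeps those subjects in safety follow-up. A loose reading of full dose is not available: Section 9.1 separates subjects with at least one full dose (FAS) from those with any amount of drug (SAS).

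**Effect of one replacement.** Let p be the true DLT probability and q = 1 − p. The values p = 1/3 and 0.40 are illustrative. Later DLTs are all counted.

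- Cohort with 1 DLT in 3, subject kept: escalation needs 0 of 3 more, q³. At p = 1/3, (2/3)³ = 0.296; at p = 0.40, 0.6³ = 0.216.
- Same cohort, that subject replaced once: q + p·q³. At p = 1/3, 0.667 + 0.333 × 0.296 = 0.765; at p = 0.40, 0.6 + 0.4 × 0.216 = 0.686.
- Phase 1b cohort with 3 of 10: not safe as it stands. If one of the three is replaced, it becomes safe with probability q, that is 0.667 or 0.60.
- Expanded cohort of 6 with one DLT subject who completed follow-up and one DLT death: 2/6 = 33%, MTD exceeded. If the death is replaced by a subject without a DLT, 1/6 = 17%, escalate.

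**Overall effect.** Let f be the share of DLT subjects who are replaced. The documents do not give f, so it is an assumption. The DLT probability among counted subjects becomes p′ = p(1 − f)/(1 − pf). With q′ = 1 − p′, P(escalate) = q′³ + 3p′q′² × q′³, and P(Phase 1b safe) = P(X ≤ 2) for X ~ Binomial(10, p′).

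For f = 0 and p = 1/3: 0.2963 + 0.4444 × 0.2963 = 0.428.

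| f (assumed) | p′ at p = 1/3 | Escalate | Phase 1b safe |
|---|---|---|---|
| 0 | 0.333 | 0.428 | 0.299 |
| 2% | 0.329 | 0.437 | 0.310 |
| 5% | 0.322 | 0.450 | 0.326 |
| 10% | 0.310 | 0.473 | 0.356 |
| 25% | 0.273 | 0.551 | 0.459 |
| 50% | 0.200 | 0.709 | 0.678 |

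At p = 0.40, f = 0, 2%, 5% and 10% give escalation 0.309, 0.317, 0.330 and 0.351, and Phase 1b safe 0.167, 0.175, 0.188 and 0.211.

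**The case against.** The strongest reply is that nobody would read the protocol this way. Section 5.4.2 describes a DLT period of up to 28 days, so a subject who dies of a DLT has been fully assessed. Table 3 also makes failure to receive the planned doses because of toxicity a DLT, whatever the grade, which covers case (a) a second time and shows that toxicity-related incomplete dosing is meant to count. The Table 3 definition of the MTD and the MTD-exceeded rule in 3.1.1.1 refer to the cohort rather than to evaluable subjects. Escalation is agreed in calls with investigators (5.4.5, 8.7). The design sections keep DLT subjects only by implication, and 3.3.2 is permissive. The large conditional probabilities presuppose a rare event.

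Much of this is fair as to likelihood: mechanical use of 9.2.1 is improbable, and the overall shift is modest unless such events form a large share of DLTs. It does not remove the conflict. Defining an event as a DLT does not say whether the subject stays in the denominator, and Section 5.4.5 has the calls adjudicate events, not evaluability. The first-three rule and the Phase 1b rule both say evaluable, and only 9.2.1 defines that term.

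Two limits stand. The definition sits in the Phase 1a paragraph of 9.2.1, so carrying it to Phase 1b assumes that the same term has the same meaning there. And a subject who has a DLT and then withdraws consent is an open case rather than a clear contradiction, since the synopsis lists consent withdrawal among the non-DLT reasons.

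**Conclusion.** The concern holds. Section 9.2.1 is wrong as written: followed literally, it replaces subjects with a DLT reaction that stops the first infusion or a DLT death before Day 28, against the other three places that deal with replacement. The affected group is narrow but severe, and the bias is always toward escalation or a finding of safe. When such a subject is the one DLT in a cohort of 3, replacement raises the chance of escalation by about 47 percentage points at a true rate of 1/3 (0.765 − 0.296 = 0.469). Averaged over all cohorts, the rise is about 1 to 5 points for an assumed 2% to 10% of DLT subjects replaced (0.437 − 0.428 = 0.009; 0.473 − 0.428 = 0.045), and larger only for shares that would be surprising. If the synopsis, 3.1.1.1 and 3.3.2 govern, there is no bias in cases (a) and (b).

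**What to change.** Reconcile Section 9.2.1 with the synopsis and Sections 3.1.1.1 and 3.3.2 through one definition, stated to apply to both the 3 + 3 rule and the Phase 1b rule:

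- A subject who received any amount of NC762 and had a DLT within the 28-day window is evaluable and is not replaced.
- The full-dose and 28-day follow-up conditions apply only to subjects without a DLT.
- Say explicitly whether the first point also holds when consent is later withdrawn or follow-up is lost. I recommend that it does, since the DLT has already been observed.

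The cost is wording in 9.2.1 and cross-references from the synopsis, 3.1.1.1, 3.1.1.2 and 3.3.2. No visit is added, no DLT criterion or treatment rule changes, and the maximum of 30 evaluable subjects in Phase 1a is unaffected.
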